#### **5.6.5 5.6.6 Physical examination**

...

*For subjects diagnosed with Malaria at Screening, physical examination should be postponed until at least 5 days after completion of Malaria treatment.*

*(Amended 06 May 2015.)*

During all other study visits, perform a physical examination only if the subject indicates during questioning that there might be some underlying pathology(ies) or if deemed necessary by the Investigator or delegate. ~~If a physical examination is performed during one of these visits, collected information will not need to be recorded in eSource.~~

*(Amended 06 May 2015.)*

...

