#### **5.4. General study aspects**

Supplementary study conduct information not mandated to be present in this protocol is provided in the accompanying manuals. The manuals provide the Investigator and the site personnel with administrative and detailed technical information that does not impact the safety of the subjects.

**5.5. Outline of study procedures****5.5.1. List of study procedures****Table 5 List of study procedures during visits to the vaccination centre (Amended 06 May 2015)**

Type of contact	Visit	Visit	Visit	Visit	Visit	Contact *	Visit	Visit	Visit	Contact *	Visit
Timepoint	Screening 	Day 0 	Day 3	Day 6	Day 30	Month 3	Month 6	Month 6 + 6 days	Month 6 + 30 days	Month 9	Month 12
Informed consent	•										
Informed assent 	•										
RDT for Malaria	•										
Malaria treatment 	•										
Inclusion/exclusion criteria 	•	•									
Demographic data	•										
Medical history 	•	•									
Physical examination (including vital signs  )	• 	• 	0	0	0		•	0	0		0
Pregnancy test 	•	• 					•				
Pre-vaccination body temperature		•					•				
Check contraindications to vaccination		0					0				
Study group and treatment name allocation 		0					0				
Vaccination		•					•				
Recording of administered treatment number		0					0				
30 minutes post-vaccination observation		0					0				
Blood sampling:											
Blood for haematology/ biochemistry	• 		•	•	•		•	•	•		•
Blood for humoral immunity		•			•		•		•		•
Blood for CMI 		•			•		•		•		•
Safety assessment:											
Record solicited AEs (day 0 to day 6)		•	•	•			•	•			
Record unsolicited AEs (day 0 to day 29)		•	•	•	•		•	•	•		
Record AEs of specific interest (clinical symptoms of thrombocytopenia)			•	•							
Record SAEs	• 	•	•	•	•	•	•	•	•	•	•
Record pregnancies		•	•	•	•	•	•	•	•		

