**CONFIDENTIAL**

202090 (EBOLA Z CHAD3-004)  
Protocol Amendment 2 Final

Type of contact	Visit	Visit	Visit	Visit	Visit	Contact *	Visit	Visit	Visit	Contact *	Visit
Timepoint	Screening 	Day 0 	Day 3	Day 6	Day 30	Month 3	Month 6	Month 6 + 6 days	Month 6 + 30 days	Month 9	Month 12
Record concomitant medications/ products/ vaccinations 		•	•	•	•	•	•	•	•	•	•
Screening Conclusion	•										
Study Conclusion											•

~ = approximately; **AE** = adverse event; **CMI** = cell-mediated immunity; **CRO** = Contract research organisation; **EVD** = Ebola virus disease; **GSK** = GlaxoSmithKline; **RDT** = *Rapid*

**Diagnostic Test**; **SAE** = serious adverse event

• is used to indicate a study procedure that requires documentation in eSource.

○ is used to indicate a study procedure that does not require automatic transfer of the study data fields from the source database into the study database at the CRO.

\* Home visit by field worker or phone call.

 The Screening visit and the Day 0 visit may take place on the same day (allowed interval 0 to 30 days).

 Refer to [Section 5.6.6](#) for the specific assessments included in the physical examination.

 Only if Visit 1 and Screening take place on a different day.

 Only for women of childbearing potential.

 Only if Visit 1 takes place more than 1 week after the Screening Visit.

 Treatment name allocation with randomisation at Day 0; treatment name allocation without randomisation at Month 6.

 Only for subjects in the sub-cohort for cell-mediated immunity (CMI).

 From Screening to Day 0, only those SAEs that are considered related to study participation or to concurrent use of GlaxoSmithKline (GSK) medication/ vaccine need to be recorded.

 Concomitant medications/ products/ vaccinations as described in [Section 6.7.1](#) and [6.7.2](#) need to be recorded in eSource.

 Only for subjects in the oldest age stratum (13 to 17 year olds) and younger subjects as per local requirements.

 **Subjects diagnosed with Malaria at Screening must receive antimalarial treatment according to local/ national standards (e.g., a 3-day treatment course of artemisinin-based combination therapy), during the Screening period.**

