***(Amended 06 May 2015.)***

### **5.6.6. Physical examination**

Perform a complete physical examination of the subject at the Screening, the Day 0, and the Month 6 visit, including assessment of height, weight, body temperature and resting vital signs: heart rate, respiratory rate after at least 10 minutes of rest, and an assessment of the following systems: head/ neck/ thyroid; eyes/ ears/ nose/ throat (EENT); respiratory; cardiovascular; lymph nodes; abdomen; skin; musculoskeletal; and neurological. Breast, anorectal, and genital examinations will be performed when medically indicated. Collected information needs to be recorded in eSource (height only needs to be recorded at Screening).

***For subjects diagnosed with Malaria at Screening, physical examination should be postponed until at least 5 days after completion of Malaria treatment.***

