***(Amended 06 May 2015.)***

During all other study visits, perform a physical examination only if the subject indicates during questioning that there might be some underlying pathology(ies) or if deemed necessary by the Investigator or delegate.

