**9.1.5. Adverse events of specific interest****9.1.5.1. Clinical bleeding within 7 days post-vaccination at Day 0**

*In the Phase 1 studies with the investigational ChAd3-EB0-Z vaccine in healthy adults, transient decreases in thrombocyte counts were observed. These decreases occurred mostly on Day 1 after vaccination and generally returned to baseline by Day 7. Although most of these decreases remained within the normal range, the as per protocol criteria for thrombocytopenia (thrombocyte count of  $< 150 \times 10^3/\mu\text{L}$ ) were met for 2.6% (7 out of 270) of the vaccinated subjects. None of the decreases in thrombocyte counts or the cases of thrombocytopenia were clinically significant, i.e., no clinical signs or symptoms suggestive of increased tendency to bleed were reported in any of the subjects. Please refer to the IB for more information.*

*In the current study, a more vulnerable population (children) will be enrolled and the acceptable limit for the thrombocyte count for study eligibility (thrombocyte count of  $\geq 100 \times 10^3/\mu\text{L}$  is acceptable) will be lower as compared to the Phase 1 studies. In addition, in order to ensure enhanced vigilance from the Investigators, clinical bleeding events (according to the Standardised MedDRA Query clinical haemorrhage) within 7 days after vaccination at Day 0 will be recorded and reported as AEs of specific interest (clinical symptoms of thrombocytopenia).*

*(Amended 06 May 2015.)*

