### **9.3.3. Evaluation of adverse events and serious adverse events**

#### **9.3.3.1. Active questioning to detect adverse events and serious adverse events**

As a consistent method of collecting AEs, the subject and/ or the subject's parent(s)/ LAR(s) should be asked a non-leading question such as:

*'Have you felt different in any way since receiving the vaccine or since the previous visit?'**'Has your child acted differently or felt different in any way since receiving the vaccine or since the last visit?'*

When an AE/SAE occurs, it is the responsibility of the Investigator to review all documentation (e.g., hospital progress notes, laboratory and diagnostics reports) relative to the event. The Investigator will then record all relevant information regarding an AE/ SAE in eSource. The Investigator is not allowed to send photocopies of the subject's medical records instead of appropriately completing in eSource. However, there may be instances when copies of medical records for certain cases are requested by GSK Biologicals. In this instance, all subject identifiers will be blinded on the copies of the medical records prior to submission.

The Investigator will attempt to establish a diagnosis pertaining to the event based on signs, symptoms, and/or other clinical information. In such cases, the diagnosis should be documented as the AE/SAE and not the individual signs/ symptoms.

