## **11. STATISTICAL METHODS**

### **11.1. Primary endpoints**

- Occurrence of each solicited local and general AE, during a 7-day follow-up period after each vaccination in all subjects, in both groups.
- Occurrence of any unsolicited AE, during a 30-day follow-up period after each vaccination (*i.e.*, the day of vaccination and 29 subsequent days), in all subjects, in both groups.

- Occurrence of haematological (CBC, including differential count and platelet count) and biochemical (ALT, creatinine) laboratory abnormalities at Screening, Day 3, Day 6, Day 30, Month 6, Month 6 + 6 days, Month 6 + 30 days and Month 12 in all subjects in both groups.
- ***Occurrence of clinical symptoms of thrombocytopenia (AE of specific interest), during a 7-day follow-up period after vaccination at Day 0 (i.e., Day 0 up to Day 6), in all subjects, in both groups.***  

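### At Day 3 and Day 6 the bleeding endpoint is recorded without a bleeding question or a required look at skin and mouth, so low-grade signs can be missed and the AESI rate understated

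*Protocol*

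**What the plan says.** Protocol 11.1 lists as a primary endpoint: "Occurrence of clinical symptoms of thrombocytopenia (AE of specific interest), during a 7-day follow-up period after vaccination at Day 0". Section 9.1.5.1 gives the reason. After the platelet falls seen in Phase 1, and "in order to ensure enhanced vigilance from the Investigators, clinical bleeding events" within 7 days of the Day 0 vaccination are to be recorded and reported as AESIs. The Table 5 row "Record AEs of specific interest (clinical symptoms of thrombocytopenia") is marked at Day 3 and Day 6 only.

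The plan provides these ways of finding such events at the two visits:

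- **Examination.** Section 5.6.6: "Perform a complete physical examination of the subject at the Screening, the Day 0, and the Month 6 visit". For the rest: "During all other study visits, perform a physical examination only if the subject indicates during questioning that there might be some underlying pathology(ies"). The investigator or a delegate may also examine at discretion.
- **Questioning.** Under 9.3.3.1 the subject and/or parent "should be asked a non-leading question such as" whether the child has felt or acted differently.
- **Solicited symptoms.** Tables 16 and 17 contain no bleeding or bruising item.
- **Diary Card and home visits.** Section 5.6.14.1 excludes AESIs from the Diary Card. A Grade 3 AE is the only home-visit finding it names as bringing the child to a clinician.
- **Unsolicited AEs.** Section 5.6.14.2 describes their capture as passive.

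SAP version 2.0, Appendix 3, lists petechiae, ecchymosis, purpura, gingival bleeding and conjunctival haemorrhage among the AESI terms. Under SAP 15.1, every vaccinated child is in the denominator and a child with no report counts as not having the event.

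**The concern.** Several of the counted signs are found by looking or by asking about them. A parent who sees a few petechiae, or slight gum bleeding, may not think of it when asked whether the child has been different. No section turns the aim of greater vigilance into a set question or check. Once a non-report is analysed as no event, a sign that was not asked about and a sign that was absent become the same data point, and this is for a primary endpoint.

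The trial is descriptive, so its output on this endpoint is an absolute rate with an exact confidence interval. That is the quantity under-ascertainment lowers. There is no second chance to measure it: SAP 15.1.4 states that AESIs are collected after the Day 0 vaccination only and are not pooled with Month 6. The evidence therefore comes from about 300 ChAd3-EBO-Z recipients, about 100 per age stratum.

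**Working it through.** **Inputs.** n = 300 per group and 100 per group per stratum (Protocol Table 4). Table 22 gives an exact 95% interval of 0.0000 to 0.0122 for 0 events in 300. Table 23 says a true proportion of 0.008 gives more than 0 events with over 90% probability. The ascertainment share s (the fraction of true events that are recorded) is not in the documents. It is an assumption here, shown over a range.

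**Reproducing the plan's figures (s = 1).**

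- Upper limit for 0 of n: 1 − 0.025^(1/n). For n = 300 this is 0.0122, as in Table 22. The other six rows of that table also reproduce to four decimals.
- Chance of at least one event: 1 − (1 − p)^300. For p = 0.008 this is 0.910, consistent with Table 23. The remaining rows of that table give 0.897 to 0.909, so they agree with 90% up to rounding of the proportions.

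**With incomplete ascertainment.** Recorded rate = s × true rate. A limit on the recorded rate becomes a limit on the true rate when divided by s. The chance of recording at least one event becomes 1 − (1 − s × p)^300.

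| s (assumed) | Upper 95% limit, 0 of 300 | Upper 95% limit, 0 of 100 | Chance of ≥ 1 recorded in 300 at true rate 0.8% |
|---|---|---|---|
| 1.00 | 1.22% | 3.62% | 91.0% |
| 0.75 | 1.22 / 0.75 = 1.63% | 3.62 / 0.75 = 4.83% | 1 − 0.994^300 = 83.6% |
| 0.50 | 1.22 / 0.50 = 2.44% | 3.62 / 0.50 = 7.24% | 1 − 0.996^300 = 70.0% |

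**Between groups.** If s is the same in both groups, the recorded difference is s × (p1 − p2) and the ratio p1/p2 is unchanged. The difference shrinks towards zero and does not change sign.

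**The case against.** There is a fair case that the gap is small.

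- AESI recording is a scheduled item at both visits, and the AE form carries an AESI field with a term list (SAP 15.1). This stands, but the field sits on the form for an adverse event. It classifies an event already found and is not described as a question put for every child.
- The investigator may examine at will, sees the child, draws blood and grades injection-site reactions. Parents are questioned, and field workers visit on the other days. All of this will bring some signs to light, and none of it is a systematic check for bleeding.
- The platelet signal does not rest on this endpoint. Platelets are counted in every child at Day 3 and Day 6, and SAP 15.4 adds percent-decrease tables and a platelet plot. Low platelet counts are themselves AESI terms. A zero bleeding count would thus be read beside good laboratory data. This is the strongest point. Still, a count does not detect bleeding, and in Phase 1 the falls were mostly on Day 1, before the first scheduled count.
- The endpoint concerns clinical symptoms, so silent signs might be thought outside it. Appendix 3 nevertheless counts petechiae and purpura when they are seen.
- Tables 22 and 23 illustrate AE rates in general, and the same division by s applies to any unsolicited AE. True; what differs here is that this event is singled out as a primary endpoint.

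A reader might infer more than the documents support:

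- **That findings at these visits need not reach the database.** The open circle ("study procedure that does not require automatic transfer of the study data fields") applies to the examination row. The AESI row has a filled circle at both visits, and 9.3.1 requires AESIs to be recorded in eSource.
- **That only a non-leading question is asked.** Solicited symptoms are also collected; none concerns bleeding.
- **That signs in toddlers cannot be reported.** Section 9.3.3.1 includes a wording for parents.
- **That events are in fact missed.** The text shows only that they can be.

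**Conclusion.** The point holds as a weakness in how a primary endpoint is ascertained. Nothing required at Day 3 or Day 6 makes anyone ask about bleeding or look for it, and silence is analysed as absence. Low-grade bleeding signs can be missed, so the absolute AESI rate may be too low.

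Its size cannot be fixed from the documents. As an illustration only, if half of the events were recorded, a zero count in 300 would exclude true rates above 2.44% and not above 1.22%; at three quarters the limit is 1.63%. This rests on an assumed ascertainment share, and on that share being alike in both groups, which the observer-blind makes likely but does not prove. On that footing the between-group difference is diluted and not reversed. Because the mitigations above are real, this is a cheap and worthwhile improvement to measurement. It is not a defect that invalidates the safety assessment.

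**What to change.** In Protocol 9.3.3.1, 5.6.6 and Table 5, add at the existing Day 3 and Day 6 visits:

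1. One direct Yes/No question on bleeding or bruising since vaccination, put to the child and/or parent and recorded in eSource for every child. State that it is an exception to the non-leading rule.
2. A brief visual check of skin and mouth, with a field showing that it was done.
3. The site of any bruise, so that venepuncture bruises can be separated.

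In SAP 15.1.4, report the AESI rate over children with the question answered as well as over the Total Vaccinated Cohort, by group and age stratum.

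The cost is protocol wording, a few eSource fields and a minute or two at visits where the child is already seen and bled. No visit or sample is added. The downside is that more minor and venepuncture bruises will be recorded in both groups.

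If the visits are already done, the report should state that ascertainment of bleeding was passive and give the number of children examined at Day 3 and at Day 6. That count may have to be taken from eSource, since the examination row is not set for automatic transfer.

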**5.6.11 Sampling**

...

- *A blood sample (fingerprick) will be taken at Screening for Malaria RDT.*  
*(Amended 06 May 2015.)*
- ...
- A volume of approximately  $\pm 0.5$  to  $\pm 1.5$  mL (*depending on the age of the child*) of whole blood should be drawn from all subjects for each analysis of haematology† *and each analysis of* biochemistry parameters at each pre-defined timepoint.  
*(Amended 06 May 2015.)*

**5.6.14 Recording of adverse events, serious adverse events and pregnancies**

- Refer to Section 9.3 for procedures for the Investigator to record AEs, serious adverse events (SAEs), and pregnancies. Refer to Section 9.4 for guidelines and how to report *AEs of specific interest (clinical symptoms of thrombocytopenia)*, SAEs, and pregnancies to the CRO (Quintiles).  
*(Amended 06 May 2015.)*

...

**5.6.14.1 Diary Card for follow-up adverse events occurring from day 0 to day 6 after vaccination**

Subjects in the sub-cohort for follow-up of AEs and assessment of humoral immunity will be followed up for AEs on a daily basis during the 7-day follow-up period after vaccination. During this period, AEs *with the exception of AEs of specific interest (clinical symptoms of thrombocytopenia)* will be recorded on a Diary Card.

*(Amended 06 May 2015.)*

...

**5.7.2 Biological samples****Table 7 Biological samples (Amended 06 May 2015.)**

Sample type	Quantity	Unit	Age strata	Timepoint	Sub-cohort *	Number of subjects
Blood for Malaria Screening	Fingerprick	NA	1 to 17 years	Screening	All screened subjects	> 600
Blood for haematology/ biochemistry	1 to 2 0.5 to 1.5	mL	1 to 17 years	Screening Day 3 Day 6 Day 30 Month 6 Month 6 + 6 days Month 6 + 30 days Month 12	All screened subjects    All enrolled subjects	> 600    ~600
Blood for biochemistry	0.5 to 1.5	mL	1 to 17 years	Screening Day 3 Day 6 Day 30 Month 6 Month 6 + 6 days Month 6 + 30 days Month 12	All screened subjects    All enrolled subjects	> 600    ~600
...						

... NA = not applicable

**5.7.3 Laboratory assays**

...

In addition to the assays described below, other tests to characterise the safety and/ or the immunogenicity of the investigational ChAd3-EBO-Z vaccine may be performed if deemed necessary for accurate interpretation of the data and/ or should such test(s) become available.

***Screening for Malaria infection will be performed using the WHO pre-qualified RDT at the site.***

***(Amended 06 May 2015.)***

**5.7.3.2 Immune response against Ebola****Table 8 Humoral immunity against Ebola (Amended 06 May 2015)**

System	Component	Method	Kit/ Manufacturer	Laboratory *
Serum	anti-GP EBOV	ELISA	TBD In-house	Quest Diagnostics

... TBD = to be determined ...

## 6. STUDY VACCINES/ PRODUCTS AND ADMINISTRATION (AMENDED 06 MAY 2015.)

### 6.1 Malaria treatment (Amended 06 May 2015.)

*All subjects diagnosed with Malaria during Screening will receive antimalarial treatment according to local/ national standards (e.g., a 3-day treatment course of artemisinin-based combination therapy), during the Screening period.*

### 6.2 Description of study vaccines

...

**Table 14 Study vaccines (Amended 06 May 2015)**

Treatment name	Vaccine/ Product name	Formulation	Presentation	Volume to be administered	Number of doses
ChAd3-EBO-Z	ChAd3-EBO-Z	ChAd3-EBO-Z= $4.2 \times 10^{11}$ vp/mL*	Liquid in vial	0.25 mL to 1 mL **	1
Nimenrix	MenACWY-TT	PSA=5 µg TT; PSC=5 µg TT; PSW 135 =5 µg TT; PsY=5 µg TT; TT~44 µg	Powder in vial	0.5 mL ***	1
	NaCl	NaCl=150 mM	Liquid in monodose, prefilled syringe		

...

\* The dose used in this study, labelled  $2 \times 10^{11}$  vp corresponds to the dose, labelled  $1 \times 10^{11}$  vp, used in the Phase I studies that was selected for further clinical development. The difference in vp concentration on the labels of the lots used in this study and the Phase I studies is the result of a different analytical method that was used to determine the vp concentration.

\*\* The volume to be administered to children in younger age strata will depend on the dosage ChAd3-EBO-Z selected based on Phase 1 data on the concentration of the investigational ChAd3-EBO-Z vaccine and will be described in the Pharmacy Manual. the recommendation of the independent data monitoring committee as a lower vaccine dose may be selected based on safety and reactogenicity data accrued during the age de-escalation process (Refer to Section 1.2.2.1).

\*\*\* Refer to the Pharmacy Manual for the volume to be injected after reconstitution.

### 6.3 6.4 Dosage and administration of study vaccines

**Table 15 Dosage and administration (Amended 06 May 2015)**

...
-----

... IM = intramuscular; vp = viral particles

...

\*\* The volume to be administered to children in younger age strata will depend on the dosage ChAd3-EBO-Z selected based on Phase 1 data on the concentration of the investigational ChAd3-EBO-Z vaccine and will be described in the Pharmacy Manual. the recommendation of the independent data monitoring committee as a lower vaccine dose may be selected based on safety and reactogenicity data accrued during the age de-escalation process (Refer to Section 1.2.2.1).

## 7. OCCURRENCE OF SUSPECTED OR CONFIRMED EBOLA VIRUS DISEASE

...

- Case details will be captured as part of SAE reporting. *In the case of a confirmed negative result, the event may be downgraded to non-serious.*  
(Amended 06 May 2015.)

...

### 9.1.3.2 Solicited general adverse events

...

**Table 17** Solicited general adverse events (Amended 06 May 2015)

...
-----

\* Fever is defined as temperature  $\geq 37.5^{\circ}\text{C}$  /  $99.5^{\circ}\text{F}$ . Body temperature ~~will~~ **may** be measured axillary (*preferred*), oral, tympanic, or rectal.

...

### 9.1.5 Adverse events of specific interest

#### 9.1.5.1 Clinical bleeding within 7 days post vaccination at Day 0

*In the Phase 1 studies with the investigational ChAd3-EB0-Z vaccine in healthy adults, transient decreases in thrombocyte counts were observed. These decreases occurred mostly on Day 1 after vaccination and generally returned to baseline by Day 7. Although most of these decreases remained within the normal range, the as per protocol criteria for thrombocytopenia (thrombocyte count of  $< 150 \times 10^3/\mu\text{L}$ ) were met for 2.6% (7 out of 270) of the vaccinated subjects. None of the decreases in thrombocyte counts or the cases of thrombocytopenia were clinically significant, i.e., no clinical signs or symptoms suggestive of increased tendency to bleed were reported in any of the subjects. Please refer to the IB for more information.*

*In the current study, a more vulnerable population (children) will be enrolled and the acceptable limit for the thrombocyte count for study eligibility (thrombocyte count of  $\geq 100 \times 10^3/\mu\text{L}$  is acceptable) will be lower as compared to the Phase 1 studies. In addition, in order to ensure enhanced vigilance from the Investigators, clinical bleeding events (according to the Standardised MedDRA Query clinical haemorrhage) within 7 days after vaccination at Day 0 will be recorded and reported as AEs of specific interest (clinical symptoms of thrombocytopenia).*

(Amended 06 May 2015.)

